#### 9.2 SAMPLE SIZE DETERMINATION

N/A – this is a pilot study and the study team will enroll 20 subjects. The study will make 20 attempts, meaning 20 patients will be enrolled and the intervention attempted; if any patients withdraw prior to the completion of the intervention, they will not be replaced.

#### 9.3 POPULATIONS FOR ANALYSES

All patients enrolled in the study will be used in all analyses

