# 9 STATISTICAL CONSIDERATIONS

# 9.1 STATISTICAL HYPOTHESES

Primary Efficacy Endpoint(s): (1) Decrease in metabolic rate to 10% during and after hypothermic period as compared to baseline metabolic requirement, (2) Increase in oxygen levels during and after hypothermia as compared to baseline oxygen levels, (3) Decrease in carbon dioxide levels during and after hypothermia as compared to baseline carbon dioxide levels

• Secondary Efficacy Endpoint(s): Decreased inflammatory markers (CRP, ESR, D-Dimer, Ferritin) during and after hypothermia as compared to baseline

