# 9.4.2 ANALYSIS OF THE PRIMARY EFFICACY ENDPOINT(S)

The metabolic rate, p02, and pCO2 during each time point after induction of hypothermia will be compared to baseline using the Wilcoxon rank sum test.

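### No rule covers patients who die or are withdrawn, so section 9.3 cannot be met; if the sicker patients are lost, the planned unpaired comparison leans towards improvement

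*Combined protocol and SAP*

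**What the plan says.** - **Population.** Section 9.3 is one sentence: "All patients enrolled in the study will be used in all analyses".
- **Size and replacement.** Section 9.2 says "this is a pilot study and the study team will enroll 20 subjects", and of those who leave before the intervention is complete, "they will not be replaced".
- **Test.** Section 9.4.2 says that metabolic rate, pO2 and pCO2 "during each time point after induction of hypothermia will be compared to baseline", and names the Wilcoxon rank sum test. Section 9.4.3 names the same test for the inflammatory markers. This test is unpaired and accepts unequal numbers on its two sides.
- **Direction of success.** Section 9.1 looks for "Increase in oxygen levels during and after hypothermia as compared to baseline oxygen levels" and "Decrease in carbon dioxide levels during and after hypothermia as compared to baseline carbon dioxide levels". A fall in metabolic rate and in the markers also counts as success.
- **Who can be missing.** Section 7.1 keeps patients under measurement after cooling stops. Section 7.2 nevertheless lets the investigator withdraw a participant from the study for disease progression, for a newly met exclusion criterion, or for being unable to receive the full 48 hours. Exclusion criterion 5, printed in the heading of section 5.3, covers renal replacement therapy, ECMO and chest tubes. Death is foreseen in sections 8.3.1 and 8.3.2.
- **Missing values.** Section 7.3 is marked N/A. Section 10.1.8 provides for data queries only. Section 9 has no rule for death, withdrawal or a missing value.

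**The concern.** All patients are ventilated and critically ill, so loss before a later time point is foreseeable, and much of it would follow from getting worse. For such a patient section 9.3 asks for something that does not exist. What then happens is left to the default behaviour of an unpaired test: every baseline stays in, and only the remaining patients supply later values. If those who leave had worse gas exchange, the later group looks better although no individual has improved.

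The study has one arm, so no control group would show this selection. Section 10.1.6 has the DSMB review efficacy data, and section 10.1.2 lists efficacy, and a primary endpoint that has been met, among the grounds for ending the study. A distorted comparison could therefore affect a decision as well as a report.

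**Working it through.** **There is no plan figure to reproduce.** Section 9.2 gives 20 patients without alpha, power, effect or SD.

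**Inputs from the plan.** n = 20, single arm; rank sum test of each later time point against baseline; no replacement.

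**Assumed inputs, because the documents give none.** Values are in SD units, with lower meaning better, as for pCO2 (pO2 is the mirror image). The baseline-to-later correlation is r = 0.6. The correlation between death risk and a worse later value is q = 0.5, or 0 for unrelated deaths. The true shift is -0.6 or 0, with 0, 2 or 4 deaths before the time point. Improvement is declared if two-sided p < 0.05 in the favourable direction, so the nominal false-positive rate is 2.5%.

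**Step 1: bias of the estimate, in closed form.** The d patients with the highest risk scores die. For d = 4 of 20, the four largest expected normal order statistics are 1.867, 1.408, 1.131 and 0.921, which sum to 5.327. The mean score of the 16 survivors is m = -5.327/16 = -0.333.
- All baselines against survivors: bias = q × m = 0.5 × (-0.333) = -0.17 SD. For q = 0.3 to 0.7 it is -0.10 to -0.23 SD.
- Each survivor against own baseline: bias = q × (1 - r) × m = 0.5 × 0.4 × (-0.333) = -0.07 SD.

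Pairing removes the part of the selection that baseline already shows. It leaves the rest.

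**Step 2: chance of declaring improvement, by simulation** (rank sum test of 20 baselines against 20 - d later values).

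| True shift | Deaths | 0 | 2 | 4 |
|---|---|---|---|---|
| -0.6 SD | linked to worse later value | 41% | 54% | 61% |
| -0.6 SD | unrelated to the value | 42% | 39% | 34% |
| none | linked to worse later value | 0.2% | 0.7% | 1.8% |

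**Step 3: other assumptions** (r = 0.5; 0, 4 and 8 deaths).
- True effect 0.5 SD: 27%, 46%, 60% if deaths are moderately linked to a worse later state; 27%, 23%, 21% if random; 28%, 16%, 10% if linked to a better baseline.
- True effect 0.8 SD: 72%, 85%, 89% if linked to a worse later state; 73%, 63%, 55% if random.
- No effect: 0.4%, 2.5%, 7.4% if moderately linked to a worse later state; 0.5%, 10.0%, 42.8% in the extreme case where exactly the worst patients die. With r = 0.2 and four moderately linked deaths the rate is 4.9%.

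**Step 4: the alternatives under the Step 2 inputs, with linked deaths.** The signed-rank test in survivors declares a true -0.6 SD shift in about 76 to 79% of runs for 0 to 4 deaths. With no effect it rises from 2.4% to 4.5% with four deaths. Ranking deaths as worst gives about 79%, 17 to 19% and 0% for 0, 2 and 4 deaths under the true shift.

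**The case against.** The strongest case against the point has five parts.

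- **Direction.** A reader might infer that more deaths always make a declared improvement more likely. The documents do not support this, because they do not say which patients die. With deaths unrelated to the value, the chance falls, as Step 2 shows. For metabolic rate, nothing says whether dying patients run higher or lower, so the direction is open. This objection stands.
- **False positives.** A reader might also infer that a few deaths would produce a spurious finding. Under the main assumptions the rate with four linked deaths is 1.8%, below the nominal 2.5%, because an unpaired test on correlated values is conservative. This stands for those assumptions. It fails with a weaker baseline correlation, a stronger link or more deaths.
- **Visibility.** Participation lasts four days, no death rate is given, individual values are to be listed, and serious events go to the DSMB. Losses would therefore be seen. This is true, but a listing does not change the test result.
- **Pairing is not a cure.** This stands. With no effect and four linked deaths the paired test declares improvement more often (4.5%) than the planned one (1.8%). The gap in power between the tests with no deaths (79% against 41%) comes from ignoring the pairing, not from deaths.
- **Worst ranks change the question.** They turn a physiological endpoint into a composite with death, and with four deaths they leave almost no power despite a real effect. This stands against using them as a veto, but not against reporting them.

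The documents also do not say that lost patients drop out of the later group. That is the practical result of their silence.

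**Conclusion.** The point holds in conditional form. Section 9.3 cannot be carried out for a patient with no later value, no other section fills the gap, and the named test allows 20 baselines to be compared with the remaining patients only. Sections 7.1 and 7.2 also leave it unclear who stays under measurement after cooling stops early, so withdrawal matters as well as death.

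If those lost have worse values, the comparison is biased towards improvement. With four linked deaths the estimate shifts by about 0.17 SD (0.10 to 0.23 over the assumed strength of the link), and the chance of declaring a true 0.6 SD benefit goes from about 41% to 61%. If losses are unrelated to the value, that chance falls to about 34%. Neither an unconditional claim that deaths favour success nor a claim of gross false-positive inflation is supported. The correlations, effect size and number of deaths are all assumptions. The change should be made; confidence in the size is medium.

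**What to change.** In sections 9.3, 9.4.2 and 9.4.3:

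1. Reword section 9.3 so that every enrolled patient is accounted for at every time point, and define the comparison set as patients with both a baseline and a value at that time.
2. Compare each later value with the same patient's own baseline by the Wilcoxon signed-rank test, in place of the rank sum test.
3. Beside each estimate, print the number contributing, the number dead and the number withdrawn by that time point.
4. Add a sensitivity analysis that ranks patients who died before the time point as having the worst change. Report it with the main result and explain any disagreement, without a rule that lets it overturn the main result.
5. Reconcile sections 7.1 and 7.2 on whether a patient who stops cooling early stays under measurement, since this decides who is missing.

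The cost is a few lines of text, three counts per table row and one extra analysis per endpoint and time point. No additional measurements are required by items 1 to 4. The sensitivity analysis will look less favourable if deaths occur. Because pairing leaves part of the selection in place, items 3 and 4 are needed to interpret item 2.

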#### 9.4 STATISTICAL ANALYSES

### 9.4.1 GENERAL APPROACH

The following variables will be examined: Changes in metabolic rate, changes in pO2, changes in pCO2, and changes in inflammatory markers.

# 9.4.2 ANALYSIS OF THE PRIMARY EFFICACY ENDPOINT(S)

The metabolic rate, p02, and pCO2 during each time point after induction of hypothermia will be compared to baseline using the Wilcoxon rank sum test.

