### 4 STUDY DESIGN

### 4.1 OVERALL DESIGN

The hypothesis of this study is that the application of mild hypothermia to patients with COVID-19 will decrease their metabolic rate and improve their oxygen and carbon dioxide levels. This is a single site pilot study of 20 subjects. Subjects will be placed on therapeutic hypothermia for 48 hours. Changes in metabolic rate, and levels of oxygen and carbon dioxide will be compared before, during, and after hypothermia.

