#### **6** STUDY INTERVENTION

#### 6.1 STUDY INTERVENTION(S) ADMINISTRATION

#### 6.1.1 STUDY INTERVENTION DESCRIPTION

Determination of metabolic rate by the metabolic cart (noninvasive connection of the device to the ventilator for 20 minutes). Initiate hypothermia (established Northwell hypothermia status post cardiac arrest protocol) using the Arctic Sun. Gel pads will be placed on subject body to cover at least 40% of body surface area. The inner layer of gel pad is made up of a heat conductive hydrogel that changes temperature and sticks to the skin. The middle layer of the pad has channels through which water is circulated and the outer layer is designed to insulate the circulating water, allowing it to maintain a temperature. Using sterile technique, a clinician will insert a temperature probe into subjects' bladder. The machine essentially is a cooling blanket. Many clinicians would use ice bags to cool patients, however using the machine allows for more accurate temperature monitoring and precision with the cooling process. The Arctic Sun 5000® is set to a temperature of 34.5 C to lower the body temperature.

Duration of hypothermia will be 48 hours after which the subject will be rewarmed. Metabolic rate, or indirect Calorimetry, will be assessed at baseline, day 1 of hypothermia, day 2 of hypothermia before rewarming, and after full rewarming. CBC, basic metabolic profile, magnesium, phosphorus, coagulation profile, ABG, inflammatory markers would be drawn every 12 hours during hypothermia until subject has achieved full rewarming and once after full rewarming.

The entire hypothermia procedure will last 48 hours. The length of time it takes to cool the patient is a maximum of 3 hours. Once the desired temperature is reached that temperature will be maintained as tolerated by subject. The new temperature of 36.5C will be manually entered into the machine initiating re-warming. Acceptable rewarming range is a temperature of 36.5C to 37.5C. The subject body temperature rewarming is typically set over 6-8 hours. Therefore, the final 6-8 hours of the 48 hour time period is set to rewarm the subject.

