#### 6.3 MEASURES TO MINIMIZE BIAS: RANDOMIZATION AND BLINDING

N/A

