### 9.4.3 ANALYSIS OF THE SECONDARY ENDPOINT(S)

The levels of inflammatory markers measured at each time point after induction of hypothermia will be compared to baseline using the Wilcoxon rank sum test.

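### Sections 9.4.2 and 9.4.3 name an independent-samples test (Wilcoxon rank sum) for before/after values from the same patients; a paired test is needed

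*Combined protocol and SAP*

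**What the plan says.** Section 9.4.2 takes metabolic rate, pO2 and pCO2 and states that the values "during each time point after induction of hypothermia will be compared to baseline using the Wilcoxon rank sum test". Section 9.4.3 repeats this for CRP, ESR, D-dimer and ferritin: the levels at each time point "will be compared to baseline using the Wilcoxon rank sum test".

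The rest of the protocol describes a within-patient comparison:

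- Section 4.1: a single-site pilot of 20 subjects in which "levels of oxygen and carbon dioxide will be compared before, during, and after hypothermia".
- Section 6.1.1: indirect calorimetry in each patient "will be assessed at baseline, day 1 of hypothermia, day 2 of hypothermia before rewarming, and after full rewarming".
- Section 6.3: randomization and blinding are marked N/A. There is no control group.
- Section 9.4.1: the variables are "Changes in metabolic rate, changes in pO2, changes in pCO2, and changes in inflammatory markers".
- Section 9.1: every hypothesis is stated relative to baseline.

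On the number of patients, section 9.2 gives 20 without a calculation and adds that "if any patients withdraw prior to the completion of the intervention, they will not be replaced". Section 9.3 puts every enrolled patient into every analysis. Section 9 names no paired test or repeated-measures model, and no rule for a patient who lacks a later value.

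**The concern.** The rank sum (Mann-Whitney) test compares two independent samples. Applied here, it treats 20 baseline values and 20 later values as 40 different people. The endpoints are changes within a person, so the named test does not match the plan's own definition of what is analysed. The mismatch covers all three primary endpoints and all four inflammatory markers, and these tests are the only inferential analyses the plan specifies.

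With positive correlation between a patient's repeated values, differences between patients stay in the test's error term when the pairing should remove them. The pilot could then report no significant fall in metabolic rate when a paired test on the same data would show one. Changing the test after the data are seen would be an unplanned change.

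**Working it through.** **The plan's own figure.** There is none to reproduce. Section 9.2 marks sample size determination N/A, and no alpha, power, SD or correlation is stated.

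**Inputs from the documents.** At most 20 pairs (section 9.2). The only effect size is for metabolic rate: "Decrease in metabolic rate to 10% during and after hypothermic period as compared to baseline metabolic requirement" (section 9.1).

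**Assumptions.** The section 9.1 wording is read as a fall *by* 10%. Values are normal with the same SD at both times, and tests are two-sided at 5%. CV is 15, 20 or 25% and correlation ρ runs from 0 to 0.9. The standardised shift is d = 0.10/CV, which gives 0.67, 0.50 and 0.40.

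**Why pairing matters.** With n patients and SD σ, the mean change has variance 2σ²(1 − ρ)/n. An independent-samples test uses 2σ²/n, so its standard error is too large by a factor 1/√(1 − ρ). For a comparison of means, the true size of a nominal 5% test is 2Φ(−1.96/√(1 − ρ)). At ρ = 0.5 this is 2Φ(−2.77) = 0.6%. The rank tests behave in much the same way, as simulation shows.

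**Simulated size of the nominal 5% rank sum test, 20 pairs.** About 5, 2, 0.8, 0.1–0.2 and 0% at ρ = 0, 0.3, 0.5, 0.7 and 0.9. The signed-rank test stays at about 5% throughout. At ρ = −0.2 the rank sum test rises to about 7%.

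**Simulated power for a 10% fall, rank sum vs signed-rank (%), 20 complete pairs** (40,000 trials per cell, exact critical values):

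| CV | ρ = 0 | 0.3 | 0.5 | 0.7 | 0.9 |
|---|---|---|---|---|---|
| 15% | 51 vs 49 | 52 vs 64 | 52 vs 78 | 54 vs 94 | 60 vs 100 |
| 20% | 32 vs 31 | 30 vs 41 | 27 vs 54 | 24 vs 76 | 20 vs >99 |
| 25% | 22 vs 22 | 19 vs 29 | 15 vs 38 | 11 vs 57 | 6 vs 96 |

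At CV 20%, the loss is 41 − 30 = 11 points at ρ = 0.3, 54 − 27 = 27 points at 0.5 (half the available power) and 76 − 24 = 52 points at 0.7. At CV 15% the loss never reaches half: at ρ = 0.7 it is (94 − 54)/94 = 43%.

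**If 4 of 20 patients lack the later value, CV 20%** (rank sum on 20 vs 16 values, signed-rank on 16 pairs): 29 vs 24, 27 vs 32, 24 vs 43, 21 vs 64 and 19 vs 98% at the same five correlations. The signed-rank test loses at ρ = 0 because it drops the unpaired baselines. It leads from ρ = 0.3 upward at all three CVs.

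**The case against.** The mismatch itself is hard to contest. The arguments are about how much it matters.

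- *It may be a slip for signed-rank.* Quite possibly. But it stands in both sections, nothing corrects it, and an analyst who follows the plan would run the wrong test.
- *This is a pilot and nothing turns on the p-values.* There is no alpha or success rule, section 4.2 stresses feasibility, and the individual listings in section 9.4.8 keep the pairing recoverable. That lowers the stakes. Section 4.2 also wants a signal of possible effect, however, and the pre-specified result would still come from the wrong test.
- *The error is conservative.* True for positive correlation. It is not true for negative correlation, where the size exceeds 5%.
- *The range is wide.* It is. The 90-point loss appears only at CV 25% with ρ = 0.9, and nothing is lost at ρ = 0. The figures concern metabolic rate alone. For pO2 and pCO2, entry on gas-exchange thresholds (section 5.1) could narrow the baseline range and lower the correlation.
- *Missing later values are partly covered.* Section 7.1 asks that remaining procedures be completed after cooling stops and that calorimetry, blood gases and markers be taken at that point. This narrows the gap but is not an analysis rule, and section 7.2 still allows withdrawal of a patient who cannot receive the full 48 hours.

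**Conclusion.** The concern holds. Sections 9.4.2 and 9.4.3 specify an independent-samples test for paired data, and this follows from the text without any assumption about spread or correlation.

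The size of the loss does depend on assumptions, because the documents supply neither quantity. For a 10% fall in metabolic rate with 20 pairs, it runs from nothing at zero correlation, through 10 to 12 percentage points at 0.3 and 23 to 27 points at 0.5, to 40 points or more from 0.7 upward. No figure can be given for the other six endpoints, since section 9.1 states no effect size for them.

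**What to change.** In sections 9.4.2 and 9.4.3, replace the rank sum test with the Wilcoxon signed-rank test on each patient's change from baseline. Add that:

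- the Hodges-Lehmann estimate of the median change is reported with its 95% confidence interval;
- each comparison uses patients with both a baseline value and a value at that time point, and the number of pairs is given.

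In section 9.3, say that all enrolled patients form the analysis set, that each paired comparison uses those with both values, and that missing values are listed with reasons.

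The cost is three or four sentences, with no new data and no extra patients. There are three limits:

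- Unpaired patients drop out of a comparison. With 16 pairs and zero correlation this costs about 4 to 8 points of power relative to the rank sum test.
- Values may be missing because a patient deteriorated, which is why the reasons should be listed.
- The signed-rank estimate assumes roughly symmetric changes, which should be checked for the inflammatory markers.

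### Sections 9.4.2 and 9.4.3 make 21 to 33 unadjusted time-point comparisons with baseline and name no main comparison for any endpoint

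*Combined protocol and SAP*

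**What the plan says.** Section 9.4.2 states that metabolic rate, pO2 and pCO2 "during each time point after induction of hypothermia will be compared to baseline", by the Wilcoxon rank sum test. Section 9.4.3 uses the same approach for CRP, ESR, D-dimer and ferritin: "The levels of inflammatory markers measured at each time point after induction of hypothermia will be compared to baseline using the Wilcoxon rank sum test".

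The time points come from Section 6.1.1. Metabolic rate "will be assessed at baseline, day 1 of hypothermia, day 2 of hypothermia before rewarming, and after full rewarming". Blood gases and inflammatory markers are "drawn every 12 hours during hypothermia until subject has achieved full rewarming and once after full rewarming". Section 6.1.1 places rewarming after the 48 hours in one sentence and inside their final 6 to 8 hours in another. The Schedule of Activities (Section 1.3) shows day columns only.

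Sections 3 and 9.1 define the endpoints as changes both during and after hypothermia. On size, Section 9.2 says only "this is a pilot study and the study team will enroll 20 subjects", and on population Section 9.3 says "All patients enrolled in the study will be used in all analyses". The plan states no alpha, no main time point, no per-patient summary and no multiplicity rule.

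**The concern.** Three primary variables are each tested several times, and nothing says which result answers the primary question. One favourable hour on one variable could be reported as the finding.

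This matters beyond presentation. Section 10.1.2 lists meeting the primary endpoint, and efficacy that would warrant stopping, among the grounds for termination. Section 10.1.6 has the DSMB assess efficacy data at four or more time points. With 9 to 13 primary comparisons and no main one, what would count as meeting the endpoint is undefined.

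The plan also makes no joint use of repeated readings taken in the same patient at the same target temperature, although these are already scheduled and enrolment is fixed at 20 without replacement.

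**Working it through.** The plan gives no power, alpha, standard deviation or within-patient correlation, so it has no figure to reproduce. I assume two-sided 0.05 per test and show a range of correlations.

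**1. Number of tests.** Metabolic rate has 3 post-baseline readings (2 on cooling, 1 after rewarming). Let d be the number of post-baseline draws for the two gases and four markers. Primary tests = 3 + 2d; secondary tests = 4d.

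| Reading of the schedule | d | Primary | Secondary | Total |
|---|---|---|---|---|
| Rewarming after 48 h: draws at 12, 24, 36, 48 h, plus one after | 5 | 13 | 20 | 33 |
| Rewarming in the final 6–8 h: draws at 12, 24, 36 h, plus one after | 4 | 11 | 16 | 27 |
| Schedule of Activities day columns (Days 2, 3, 4) | 3 | 9 | 12 | 21 |

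**2. Chance of at least one false positive.** For k independent tests this is 1 − 0.95^k: 48.7% for 13, 81.6% for 33, 37.0% for 9 and 65.9% for 21. The tests are not independent, because those on one variable share a baseline. I therefore simulated trials with no effect: n = 20, seven variables, and equal correlation r between any two readings of a variable in one patient.

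| r | Planned rank sum, 13 primary | Planned rank sum, all 33 |
|---|---|---|
| 0 | 42% | 73% |
| 0.3 | 20% | 44% |
| 0.4 | 14% | about 30% |
| 0.5 | 9% | 21% |
| 0.6 | 5% | 12% |
| 0.7 | 1.5% | 4% |
| 0.8 | at most 1% | 1% |

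The rates fall because the rank sum test treats paired readings as independent groups and becomes conservative. Its per-test error is 4.9% at r = 0, 0.8% at r = 0.5 and 0.1% at r = 0.7.

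With a paired signed-rank test the per-test error returns to about 4.9%. The chance of at least one false positive is then about 41–43% over 13 tests and 74–75% over 33, at every r tried. On the smallest count it is 32–34% over 9 and about 60% over 21.

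**3. What averaging would gain.** Let m be the number of on-cooling readings, with equal variance s² and equal correlation r.

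- One reading minus baseline: variance 2s²(1 − r).
- Mean of m readings minus baseline: variance s²(1 − r)(m + 1)/m.
- Ratio: (m + 1)/(2m), whatever r is.

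This gives 3/4 = 0.75 for m = 2 (metabolic rate), 4/6 = 0.67 for m = 3 and 5/8 = 0.625 for m = 4 (gases and markers). The reductions are 25%, 33% and 37.5%.

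**4. How far that depends on the assumption.** Suppose instead that correlation decays with each successive reading (AR(1)). For m = 2 and ρ = 0.9, the variance of the mean minus baseline is 1 + (1 + 0.9)/2 − (0.9 + 0.81) = 0.24, in units of s². The first reading minus baseline has 2(1 − 0.9) = 0.20, so the mean is 20% worse. The second has 2(1 − 0.81) = 0.38, so the mean is 37% better. Over ρ from 0.3 to 0.9 and m from 2 to 4, the extremes are a 67% loss against the first reading and a 51% gain against the last.

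On the unpaired scale that the plan uses, the variance ratio under equal correlation is [1 + (1 + (m − 1)r)/m]/2. The reduction is then 13–19% at r = 0.5 and 3–4% at r = 0.9.

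**5. Averaging alone does not control error.** Three independent primary tests at 0.05 give 1 − 0.95³ = 14.3%, and all seven endpoints give 1 − 0.95⁷ = 30.2%.

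**The case against.** The strongest defence is that this is a 20-patient pilot on feasibility and possible efficacy, with no stated alpha or success threshold, and that individual data will be listed by measure and time point (Section 9.4.8). Formal error control is less pressing in such a study. That lowers the weight of the point, but Section 10.1.2 still attaches a consequence to meeting a primary endpoint that the analysis section does not pin down.

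A reader might infer that the plan as written carries a false-positive chance of about 75%. The documents do not support that: they specify the rank sum test, and at moderate to high within-patient correlation the chance is far lower. The 75% figure describes what follows if the test is paired and nothing else changes.

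A reader might also infer that the plan forfeits a known 25–38% of variance, equal to 20/0.75 = 27 to 20/0.625 = 32 patients. That rests on equal correlation, a constant effect during cooling and a paired analysis. None of these is documented, and Section 8.1 expects that ventilator support may be lowered during cooling. Nor can one say that the trial would otherwise fail, since no standard deviation or power target is given.

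Two further objections stand. An on-cooling mean does not cover the after-hypothermia part of the endpoints. Requiring all three primary variables to succeed is also debatable, because Section 5.1 admits patients on any one criterion, including plateau pressure alone.

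**Conclusion.** The point holds as a gap in specification. Sections 9.4.2 and 9.4.3 make 21 to 33 unadjusted comparisons, 9 to 13 of them primary, with no main comparison for any endpoint. The range reflects inconsistent schedules in the protocol.

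At an assumed 0.05 per test, the chance of at least one false positive over 33 planned tests runs from about 73% to 1% as within-patient correlation goes from 0 to 0.8. Correct pairing alone brings it to about 75%, with about 41% over 13 primary tests, so the two defects need one joint repair. These figures assume equally correlated readings and complete data on 20 patients.

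The precision gain from averaging is a reasonable expectation under stated assumptions, not a property of this trial's data.

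**What to change.** - **Main comparison.** For each endpoint, pre-specify one paired comparison: the patient's mean over the available readings at target temperature minus that patient's baseline. Use the Wilcoxon signed-rank test and report the median change with a 95% confidence interval.
- **After rewarming.** Give this value its own pre-specified secondary paired comparison and say which multiplicity family it belongs to.
- **Multiplicity.** State alpha and sidedness. Use Holm, or a stated joint rule, across the three primary variables, and Holm across the four markers.
- **Individual time points.** Show them descriptively, without tests.
- **Incomplete data.** Say how patients with few or no on-cooling readings are handled. Section 7.2 allows rewarming before 48 hours, and Section 9.3 keeps every enrolled patient in every analysis.
- **On-cooling window.** Before defining it, reconcile whether rewarming falls inside or after the 48 hours, and align Section 1.3 with Section 6.1.1.
- **Stopping language.** Tie the primary-endpoint wording in Section 10.1.2 to the main comparisons, or remove it.

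No new data are needed. The cost is revised analysis wording, plus matching endpoint wording in the Synopsis and Sections 3 and 9.1, because the after-hypothermia part moves to a secondary role. An effect confined to one time point would appear only in the descriptive display. If readings are serially correlated, the mean can be less precise than the first reading alone.
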